5. STUDY TREATMENT

All subjects entering the screening phase will receive a unique subject number. This number will be used to identify the subject throughout the study. Subjects withdrawn from the study will retain their subject number.

5.1 Treatment Schedule/Administration:

Treatment must begin within 28 days of the date the subject is entered into the CTMS (OnCore). Upon confirmation of eligibility and provision of subject study number, subjects will receive TAS-102 at the following dose and schedule. The number of tablets of each strength that are needed for the 35 mg/m² dose per BSA level is shown in Table 1.

| TAS-102 | BSA ^a | Dosage in | Total daily | Tablets per dose | |
|----------------------|-------------------|------------|-------------|------------------|-------|
| Dose | (m ²) | mg | dose (mg) | _ | |
| (2x daily) | | (2x daily) | | 15 mg | 20 mg |
| 35 mg/m ² | < 1.07 | 35 | 70 | 1 | 1 |
| | 1.07 - 1.22 | 40 | 80 | 0 | 2 |
| | 1.23 - 1.37 | 45 | 90 | 3 | 0 |
| | 1.38 - 1.52 | 50 | 100 | 2 | 1 |
| | 1.53 - 1.68 | 55 | 110 | 1 | 2 |
| | 1.69 - 1.83 | 60 | 120 | 0 | 3 |
| | 1.84 - 1.98 | 65 | 130 | 3 | 1 |
| | 1.99 - 2.14 | 70 | 140 | 2 | 2 |
| | 2.15 - 2.29 | 75 | 150 | 1 | 3 |
| | ≥2.30 | 80 | 160 | 0 | 4 |
| | | | | | |

 Table 1. Dose Calculations Based off BSA

a Calculate body surface area (BSA) to 2 decimal places.

Each treatment cycle will be 28 days in duration. One treatment cycle consists of the following:

Days 1 through 5: TAS-102 ($35 \text{ mg/m}^2/\text{dose}$) orally 2 times daily with the first dose administered in the morning of Day 1 of each cycle and the last dose administered in the evening of Day 5.

Days 6 through 7: Rest

Days 8 through 12: TAS-102 (35 mg/m²/dose) orally 2 times daily with the first dose administered in the morning of Day 8 of each cycle and the last dose administered in the evening of Day 12.

Days 13 through 28: Rest

The patient must be instructed in the handling of study medication as follows:

- To store the study medication at room temperature
- To only remove from the study medication kit the amount of tablets needed at the time of dosing
- Not to remove doses in advance of the next scheduled dosing
- To make every effort to take doses on schedule
- To take study medication within 1 hour after completing a meal (morning and evening meals) with a glass of water per the dose schedule
- If the patient vomits after taking study medication, the patient should not take another dose.

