- To keep study medication in a safe place and out of reach of children

To bring all used and unused study medication kits to the site at each visit Any missed doses reported by the subject should be recorded in the subject's source documents. Subjects should not take additional doses to make up for missed or held doses.

Complete blood count (CBC) with differential will be checked on the first day of each cycle, every 28 days, or within 72 hours of each cycle upon completion of Cycle 1 to accommodate subjects with long travel distance and on Day 15 of each cycle to monitor for development of anemia and neutropenia. In the absence of significant treatment-related abnormalities, and documentation of an ANC greater than or equal to 1500/ mm³ and platelet count of greater than or equal to 75,000/ mm³ treatment cycles will continue every 28 days until subject intolerance, subject discontinuation, or disease progression. Tumor status will be assessed every two cycles.

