5.4.1 Dose Modification Explained

Subjects are permitted dose reduction(s) to a minimum dose of 20 mg/m^2 (40 mg/m^2 /day) in 5 mg/m² (10 mg/m^2 /day) steps. A maximum of three dose reductions in decrements of 5 mg per square meter are allowed for toxicity to a minimum dose of 20 mg/m^2 . Do not escalate dose once it has been reduced. Refer to Table 2 located in this sub-section.

Table 2: TAS-102 Dose Modification Table

| tot at white | 1 | Dosage in | An and a second | Tablets | per dose | Cards I | oer Cycle |
|----------------------------|--------------------------|-----------------------------|--------------------------|---------------------|---------------------|---------|-----------|
| TAS-102 Dose (2x daily) | BSA (m ²) | mg (2x daily) | Total daily dose (mg) | 15 mg | 20 mg | 15 mg | 20 mg |
| Level 1 Dose Red | uction: From 3 | 5 mg/m ² to 30 | mg/m ² | | | | |
| 30 mg/m^2 | < 1.09 | 30 | 60 | 2 | 0 | 2 | 0 |
| | 1.09 - 1.24 | 35 | 70 | 1 | 1 | 1 | 1 |
| | 1.25 - 1.39 | 40 | 80 | 0 | 2 | 0 | 2 |
| | 1.40 - 1.54 | 45 | 90 | 3 | 0 | 3 | 0 |
| | 1.55 - 1.69 | 50 | 100 | 2 | 1 | 2 | 1 |
| | 1.70 - 1.94 | 55 | 110 | 1 | 2 | 1 | 2 |
| | 1.95 - 2.09 | 60 | 120 | 0 | 3 | 0 | 3 |
| | 2.10 - 2.28 | 65 | 130 | 3 | 1 | 3 | 1 |
| | ≥ 2.29 | 70 | 140 | 2 | 2 | 2 | 2 |
| Level 2 Dose Redu | ection: From 30 | 0 mg/m ² to 25 | mg/m ² | | | | |
| 25 mg/m^2 | < 1.10 | 25 ^a | 50 ^a | 2 (PM) ^a | 1 (AM) ^a | 2 | 1 |
| | 1.10 - 1.29 | 30 | 60 | 2 | 0 | 2 | 0 |
| | 1.30 - 1.49 | 35 | 70 | 1 | 1 | 1 | 1 |
| | 1.50 - 1.69 | 40 | 80 | 0 | 2 | 0 | 2 |
| | 1.70 - 1.89 | 45 | 90 | 3 | 0 | 3 | 0 |
| | 1.90 - 2.09 | 50 | 100 | 2 | 1 | 2 | 1 |
| | 2.10 - 2.29 | 55 | 110 | 1 | 2 | 1 | 2 |
| | \geq 2.30 | 60 | 120 | 0 | 3 | 0 | 3 |
| Level 3 Dose Redu | iction: From 25 | 5 mg/m ² to 20 i | mg/m ² | | | | |
| 20 mg/m^2 | < 1.14 | 20 | 40 | 0 | 1 | 0 | 1 |
| | 1.14 - 1.34 | 25 ^a | 50 ^a | 2 (PM) ^a | 1 (AM) ^a | 2 | 1 |
| | 1.35 - 1.59 | 30 | 60 | 2 | 0 | 2 | 0 |
| | 1.60 - 1.94 | 35 | 70 | 1 | 1 | 1 | 1 |
| | 1.95 - 2.09 | 40 | 80 | 0 | 2 | 0 | 2 |
| | 2.10 - 2.34 | 45 | 90 | 3 | 0 | 3 | 0 |
| | ≥ 2.35 | 50 | 100 | 2 | 1 | 2 | 1 |

^a At a total daily dose of 50 mg, patients should take 1 x 20-mg tablet in the morning and 2 x 15-mg tablets in the evening.

BSA=body surface area (calculate to 2 decimal places)

5.4.2 Non-Hematologic Toxicity

Refer to Table 3 located in this sub-section.

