These toxicities can be AEs or laboratory abnormalities such as hepatobiliary or renal laboratory findings.

| Grade ^a | Dose Hold/Resumption within a 28-day Treatment Cycle | Dose Adjustment for Next Cycle |
|--------------------------------|--|-----------------------------------|
| Grade 1 or 2 | | |
| Any occurrence | Maintain treatment at the | None |
| | same dose level | |
| Clinically concerning or treat | tment-related Grade 3 ^b or high | er |
| 1st, 2nd, or 3rd | Suspend treatment until | Reduce by 1 dose level from |
| occurrence | Grade 0 or 1 | the previous level |
| | | |
| 4th occurrence | Discontinue treatment | Discontinue treatment |

Table 3: TAS-102 Dose Modification Schedule for Non-hematologic Toxicities

a Note: For toxicities (AEs or laboratory abnormalities) considered unlikely to become serious or life-threatening (including, but not limited to, fatigue, alopecia, changes in libido, and dry skin), subjects may continue on study medication at the same dose without reduction or interruption at the discretion of the Investigator (irrespective of grade).

b Except for Grade 3 nausea and/or vomiting controlled by aggressive antiemetic therapy or diarrhea responsive to antidiarrheal medication. If there is any uncertainty about continuing study medication or resuming study medication in a subject with Grade \geq 3 non-hematologic toxicities, the case must be discussed with the UFHCC Data and Safety Integrity Committee (DISC) prior to continuing treatment.

5.4.3 Hematologic Toxicity

Obtain complete blood cell counts prior to and on Day 15 of each cycle.

Do not initiate the cycle of LONSURF[®] until:

- Absolute neutrophil count (ANC) is greater than or equal to 1,500/mm³ or febrile neutropenia is resolved
- Platelets are greater than or equal to 75,000/mm³
- Grade 3 or 4 non-hematological adverse reactions are resolved to Grade 0 or 1

Within a treatment cycle, withhold LONSURF[®] for any of the following:

- Absolute neutrophil count (ANC) less than 500/mm³ or febrile neutropenia
- Platelets less than 50,000/mm³
- Grade 3 or 4 non-hematological adverse reactions

After recovery, resume LONSURF[®] after reducing the dose by 5 mg/m²/dose from the previous dose level, if the following occur:

- Febrile neutropenia

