- Uncomplicated Grade 4 neutropenia (which has recovered to greater than or equal to 1,500/mm³) or thrombocytopenia (which has recovered to greater than or equal to 75,000/mm³) that results in more than 1-week delay in start of next cycle

• Non-hematologic Grade 3 or Grade 4 adverse reaction except for Grade 3 nausea and/or vomiting controlled by antiemetic therapy or Grade 3 diarrhea responsive to antidiarrheal medication

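### Table 3 and Section 5.4.3 place the dose reduction for Grade 3–4 non-hematologic toxicity at different times, so the dose on resuming within the same cycle is not settled

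*Combined protocol and SAP*

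**What the plan says.** Section 5.4.1 sets the general frame: "A maximum of three dose reductions in decrements of 5 mg per square meter are allowed for toxicity", down to 20 mg/m² per dose, and "Do not escalate dose once it has been reduced".

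Table 3 in Section 5.4.2 deals with non-hematologic toxicity in two columns. For the first three occurrences at Grade 3 or higher, the within-cycle column says only that treatment is suspended until the event is back to Grade 0 or 1. The one-level reduction stands in the other column, "Dose Adjustment for Next Cycle". A fourth occurrence ends treatment.

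Section 5.4.3 is titled for hematologic toxicity but also has drug withheld within a cycle for Grade 3 or 4 non-hematologic reactions. After recovery the drug is resumed "after reducing the dose by 5 mg/m²/dose from the previous dose level, if the following occur", and one listed trigger is "Non-hematologic Grade 3 or Grade 4 adverse reaction except for Grade 3 nausea and/or vomiting controlled by antiemetic therapy" (responsive Grade 3 diarrhea is also excepted).

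Section 6.2 repeats the hold until Grade 0 or 1 and gives no dose for resumption. On the calendar, Section 5.1 doses on Days 1–5 and 8–12, then "Days 13 through 28: Rest", and adds that "Subjects should not take additional doses to make up for missed or held doses".

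**The concern.** The two sections cover the same events and attach the reduction to different moments: the next cycle in Table 3, the first dose after the hold in 5.4.3. Neither refers to the other. The 5.4.3 rule also sits under a heading where a site handling a non-hematologic event may not look.

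Two subjects with the same event and the same recovery could therefore resume at different doses. Section 11.2 plans safety summaries by dose level and fitted dose-toxicity curves. A later event in that cycle would be assigned to 35 or to 30 mg/m² according to which section the site had read, not according to anything about the subject.

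**Working it through.** **Inputs.** Starting dose 35 mg/m² twice daily on 10 days per cycle (Section 5.1), so 20 doses and 20 × 35 = 700 mg/m² planned per cycle. Step size 5 mg/m², at most three steps (Section 5.4.1). No dosing after Day 12 and no make-up doses (Section 5.1). Tablet doses from Tables 1 and 2.

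**The plan's own figure.** 35 − 3 × 5 = 20 mg/m² per dose, or 2 × 20 = 40 mg/m²/day. This matches the minimum in Section 5.4.1.

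**First event at 35 mg/m², resumption in the same cycle.** Table 3's layout implies 35 mg/m² until the next cycle, since it places no reduction in the within-cycle column. Section 5.4.3 gives 35 − 5 = 30 mg/m². The difference is 5 mg/m² times the number of doses left:

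| Resume on | Doses left | At 35 (mg/m²) | At 30 (mg/m²) | Difference (mg/m²) | Share of 700 |
|---|---|---|---|---|---|
| Day 3 | 16 | 560 | 480 | 80 | 11.4% |
| Day 8 | 10 | 350 | 300 | 50 | 7.1% |
| Day 10 | 6 | 210 | 180 | 30 | 4.3% |
| Day 12 | 2 | 70 | 60 | 10 | 1.4% |
| Day 13 or later | 0 | 0 | 0 | 0 | 0% |

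**Next cycle.** Table 3 alone: 35 − 5 = 30 mg/m². Section 5.4.3 alone: 35 − 5 = 30 mg/m². There is no difference.

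**In tablets, BSA 1.75 m².** Table 1 gives 60 mg at 35 mg/m² (band 1.69–1.83). Table 2 gives 55 mg at 30 mg/m² (band 1.70–1.94). Resuming on Day 8: 10 × 60 = 600 mg against 10 × 55 = 550 mg. The gap of 50 mg is 50/1,200 = 4.2% of the planned 20 × 60 = 1,200 mg. It is smaller than the nominal 7.1% because the tables round to whole tablets: the step is 5 mg here, against 5 × 1.75 = 8.75 mg unrounded.

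**The case against.** Four points can be made on the other side.

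**Table 3 never says to resume at the same dose.** Where it means an unchanged dose it says so, in the Grade 1–2 row and in footnote a. The sections can therefore be read together: 5.4.3 supplies the resumption dose, and Table 3 confirms that the next cycle is one level below the level at which the event occurred. This stands in part. The 60 mg figure is an inference from the column layout, not a stated dose. But the combined reading is not stated either.

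**Footnote b of Table 3 sends uncertainty about continuing or resuming to the DISC.** This softens the problem. However, it concerns whether to go on, not at what dose, and it works only if the site notices a doubt. A site that reads one section has none.

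**The exposure is narrow.** The subject must reach Grade 3 or 4, recover to Grade 0 or 1 and resume by Day 12. Controlled nausea or vomiting and responsive diarrhea are exempt in both sections. Table 4 schedules adverse event assessment before each cycle, with only a blood count on Day 15. This stands, and it limits the size of the point.

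**A reader might infer that one event costs two permanent reductions**: one on resumption under 5.4.3 and a second at the next cycle under Table 3, so 35 to 30 to 25 mg/m² (60 to 45 mg at BSA 1.75, a cut of 15/60 = 25%). The documents do not support this. Neither section instructs two steps. One step per event gives 30, 25 and 20 mg/m² after three events, which fits both the limit of three reductions and Table 3's three occurrences before discontinuation. Two steps per event would give 25, 15 and 5 mg/m², using 2, 4 and 6 reductions, and would break the limit and the minimum at the second event. What remains is a risk of misreading. The previous level is not defined, no sentence says that a reduction on resumption is the same one as Table 3's next-cycle reduction, and a reduction made in error could not be reversed under 5.4.1.

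**Conclusion.** The inconsistency is real and limited. Table 3 and Section 5.4.3 place the reduction at different times for the same Grade 3–4 non-hematologic event, and nothing in the protocol says which governs resumption within the cycle. For a first event the nominal gap is 5 mg/m² per remaining dose: 1.4% of the planned cycle dose if dosing resumes on Day 12, 7.1% on Day 8 and 11.4% on Day 3. It is zero if the subject cannot resume by Day 12.

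These figures assume a first event at 35 mg/m² and take Table 3's silence as no reduction before the next cycle. The documents do not say how often subjects would recover in time, so the number affected cannot be estimated. The consequences lie in the resumed doses and in the dose level assigned to later events in the Section 11.2 summaries. No effect on the primary PFS analysis is shown. Section 6.2 already excludes per-protocol modifications when judging non-compliance, so no extra discontinuations follow on that ground. No view is taken on which timing or dose is right.

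**What to change.** Reconcile Table 3 and Section 5.4.3 so that the protocol states in one place, for Grade 3–4 non-hematologic toxicity, when the reduction takes effect, what dose applies on resumption within the same cycle, and how the two instructions relate for a single event. Define the level from which a reduction is counted. The sponsor decides the rule; the review does not favour either section.

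The cost is wording in two adjoining sub-sections, handled as a protocol amendment under Section 15.6. No procedures, visits or data items are added.

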6 TREATMENT DISCONTINUATION

6.1 Removal of Subjects From Study

Subjects who discontinue participation in the clinical study on their own or subjects who are withdrawn by the investigator, for reasons other than completion of treatment, disease progression or toxicity, will be defined as premature withdrawals.

Subjects who are not initiated on study drug, but sign informed consent and undergo at least some of the screening procedures will be considered screening failures. A record of these subjects will be maintained by the study site.

6.2 Study Treatment Discontinuation

Study treatment will be withheld under the following circumstances::

- Grade 4 neutropenia (ANC less than 500/mm³ or febrile neutropenia), until ANC is resolved to greater than 1500/mm³ or febrile neutropenia is resolved
- Grade 4 thrombocytopenia or grade 3 thrombocytopenia with bleeding (platelets less than 50,000/mm³), until platelet count resolved to greater than or equal to 75,000/mm³
- Other grade 3 or 4 non-hematologic toxicity, until the adverse reaction has resolved to Grade 0 or 1

A subject will be discontinued from protocol therapy under the following circumstances:

- Any adverse event which, in the Investigator's opinion, requires termination of the study medication.
- Disease progression, unless at the discretion of the Principal Investigator (in collaboration with any co-sponsors or collaborators) determines continued treatment with study drug is appropriate.
- Substantial non-compliance (>25% of missed doses with the exception of dose delays and dose modifications per protocol, or dose-related instructions from research team staff due to adverse events), with the requirements of the study.
- The subject presents with a beta-HCG test consistent with pregnancy and is confirmed to be pregnant. Pregnancy will be reported along the same timelines as a serious adverse event.
- The subject uses illicit drugs or other substances that may, in the opinion of the Investigator, have a reasonable chance of contributing to toxicity or otherwise interfering with the study or its results.

- The development of a second malignancy that requires treatment, which would interfere with this study.
- The subject is lost to follow-up.
- Development of an intercurrent illness or situation which would, in the judgment of the investigator, affect assessments of clinical status and study endpoints to a significant degree.

The Investigator will make every reasonable effort to keep each subject in the study unless it is in the subject's best interests to discontinue participation. If a subject is removed from the study or declines further participation, all End of Treatment evaluations should be performed if the subject is willing and able to be assessed. A description of the reason(s) for withdrawal from the study must be recorded on the case report form (CRF). The Investigator should also ensure that all subjects are followed up for survival status and progression (as applicable) after the End of Treatment Visit.

Relevant visit data should be entered on the CRF and any unused study medication will be accounted for and returned for all subjects participating in the study who receive study drug. Subjects who discontinue following study consent will have relevant information completed and recorded on the CRF. All subjects who discontinue because of adverse events or clinically significant laboratory abnormalities should be followed up until they recover or stabilize, and the subsequent outcome will be recorded. If any subject should die within 30 days of receiving study treatment, the Investigator will inform the UF Health Data Integrity and Safety Committee (DISC).

6.3 Replacement of Subjects

Subjects lost to follow up along with other clinical variables without values are considered as missing data. We are not planning to do missing data imputation. These subjects will not be replaced on the trial unless they were lost to follow-up prior to receiving a single dose of the study drug.

7 STUDY PROCEDURES

7.1 Study Schedule of Events

See Table 4 located in this section.

| | | Treatment Ph | ase ^l (1 cycle = 1 | 28 days) | End of | |
|--|---|---|--|--|--|--|
| Evaluation | Screening ^a | Before each cycle (within 3 days) | D15 of each cycle (± 3 days) | Odd # cycles (± 7 days) | treatment (within 30 days post last dose) | Follow Up |
| History & Physical | X | X | | | Х | X ⁱ |
| Performance Status | X | X | | | Х | |
| Vital Signs ^b | X | X | | | Х | |
| AE Assessment | X | X | | | Х | Xj |
| Concomitant Meds | X | X | | | Х | X^k |
| ECG ^c | X | | | | | |
| Pregnancy test ^d | X | | | | | |
| Urine analysis | X | | | | | |
| CMP ^{e,f} | X | X | | | X | |
| Magnesium | X | X | | | Х | |
| CBC w/Diff ^e | X | X | X ^m | | X | |
| PT/INR ^g | X | | | | | |
| CA19-9 | X | Х | | | | |
| CT or MRI ^h | Х | | | Х | | Х |
| Survival Status | | | | | | Х |
| a. All screening procedures s completed within 7 days o required to be repeated at b. Vital signs include height, scale). Height should be o c. ECGs will be obtained at s performed at regular inter d. Pregnancy testing will be pregnancy testing will be physical signs, or sympton | should be completed of treatment. Histor treatment initiation weight, blood pres obtained at screenin screening. Subjects vals (interval timing done for all females conducted any time ms of pregnancy. | d within 28 days of t y & Physical, Vital 3 if they were comple sure, pulse, tempera g only. who are placed on 6 g is at the discretion s of childbearing age clinical signs presen | reatment except for s Signs, ECOG PS, CM ted within 7 days pri ture and pain level (s QT prolonging media of the treating invest at Screening prior to th for potential pregn | serum pregn. I P, CBC w 1 or to Cycle ubjective 1- cations while igator). o TAS-102 i ant state, e.g | ancy testing wh Diff and CA19- 1 Day 1. 10 self-reported e on study shou nitiation. Stand | ich should be 9 are not 1 ld have ECGs lard-of-care other |

Table 4: Study Schedule and Procedures

Laboratory testing may be performed up to 72 hours prior to day 1 of the next cycle of therapy.

CMP: Na, K, Cl, CO₂, Glucose, BUN, Creatinine, Ca, Albumin, Total Bilirubin, Alk Phos, Total Protein, AST, ALT.

PT/INR should be followed closely for subjects on warfarin.

g. h. CT of the chest, abdomen and pelvis or CT of the chest and MRI of the abdomen and pelvis are allowed. Consistent imaging modality should be used throughout the study. Imaging should be performed every 8 weeks (+/- 7 days) beginning with Cycle 3 until disease progression.

H&P is required at 30 days (+7 days) following the last dose of study drug. Additional H&Ps are required as needed to follow ongoing AEs.

Adverse events should be followed for 30 days after the last dose of protocol therapy or until the initiation of subsequent treatment. AEs continuing > 30 days should be monitored until resolution.

Subjects or providers should be contacted every 3 months to assess survival status and subsequent therapies.

TAS-102 (Lonsurf[®]) is administered orally twice daily within one hour of completion of morning and evening meals on Days 1 through 5 and Days 8 through 12 of each 28-day cycle.

For CBC w/diff to be obtained at Day 15 of each cycle, notify the investigator if any of the following parameters are observed m. in the lab results: 1) ANC \leq 500 µL, 2) platelets < 50 thou/mm³, or 3) Hgb < 7 g/dL.

7.2 Screening Evaluations

Written informed consent must be obtained prior to performing any study-specific evaluations or tests. Tests or evaluations performed as standard of care within the specified screening period, but prior to informed consent, may be accepted for this study and need not be repeated.

All screening procedures should be completed within 28 days of treatment except for serum pregnancy testing which should be completed within 7 days of treatment. History & Physical, Vital Signs, ECOG PS, CMP, CBC w Diff and CA19-9 are not required to be repeated at treatment initiation if they were completed within 7 days prior to Cycle 1 Day 1.

